## 9.8 Biomarkers, Metabolomics Gene and Microbiome Analysis

- Blood samples for potential biomarkers (including but not limited to ProC3 and ELF), metabolomics and better understanding of mechanism of action will be collected at Screening, Baseline, weeks 12, 24, 48 and every 24 weeks thereafter and at early termination/study completion.
- Blood sample for gene analysis will be taken from subjects providing consent in a
  dedicated informed consent form (ICF) (subject to local regulations and approval),
  preferably at Baseline visit, but will be accepted at any other visit. Samples will be kept
  frozen for future analysis
- In the Open-Label Part, stool samples for analysis of microbiome and better understanding of mechanism of action will be collected at Baseline, weeks 4, 12, 24, 48 and 72 and at early termination (if prior to week 72).

#### 9.9 SAFETY ASSESSMENTS

#### 9.9.1 Adverse Events

AEs will be recorded as soon as the subject signs the ICF and throughout the study. AEs should be reviewed and updated at each visit.

## 9.9.2 Safety Laboratory Evaluations

Subjects should fast for 8 hours prior to each visit that includes laboratory sampling.

The central laboratory will be responsible for providing preliminary and final laboratory reports to the sites and for sending "alert" values to both the Principal Investigator and Sponsor or a designee. The PI should review, comment, sign, and date the final laboratory reports. All out-of-range and "alert" laboratory values are to be evaluated by the PI for clinical significance and classified as:

- Abnormal, not clinically significant
- Abnormal clinically significant

Any clinically significant laboratory parameters observed at screening should be documented as medical history.

A new or worsening clinically significant laboratory value observed at any time after screening should be further assessed, monitored and documented as an AE on the AE eCRF.

## 9.9.3 Clinical Laboratory Tests

Clinical laboratory tests are detailed in Table 6. They will be performed according to the schedule of activities (See Section 8.2).

Reference ranges for all laboratory parameters are provided in the laboratory manual.

Table 6: Clinical Laboratory Tests

Category	Parameters	
Serum biochemistry	Sodium, potassium, chloride, calcium, phosphorus, blood urea nitrogen (BUN), albumin, bilirubin (direct and total), ALT, AST, GGT, alkaline phosphatase, cholesterol (total cholesterol, LDL, apoB, non- HDL cholesterol and HDL cholesterol), triglycerides, hs-CRP	
Hematology Complete blood count (CBC)	Hemoglobin, Hematocrit, Red Blood Cells count (RBC), MCV, White Blood Cells count + differential, Neutrophils, Basophils, Eosinophils, Lymphocytes, Monocytes, Platelet count	
Serology	HBV, HCV (for subjects positive for hepatitis C antibodies, sustained virologic response (SVR) should be confirmed) and HIV	
Renal function	Creatinine, eGFR	
СРК	Creatine kinase	
Thyroid function	TSH, T3 and T4	
Urinalysis	pH, Blood, Glucose, Ketones, Erythrocytes, Protein, Specific Gravity (USG), Nitrite, Leukocytes, Bilirubin, Urobilinogen	
Coagulation	Fibrinogen, prothrombin time/INR, aPTT	
Glycemic Parameters		

Instructions for the preparation, handling, storage, and shipment of specimens will be detailed in the study's manual of procedure.

## 9.9.4 Electrocardiogram (ECG)

A standard 12-lead ECG will be recorded at all study visits. The subject should rest in a recumbent position for at least 10 minutes before the ECG is taken.

The ECG will be evaluated by the Investigator at the time of performance (signed and dated) and the printout should be kept in the source documentation file. Additionally, until the Sponsor instructs otherwise, starting from the baseline visit all ECGs will also be sent to a central ECG laboratory. The centralized review will be done by a cardiology specialist who will provide an ECG report and notifications to the site. The report will provide an overall interpretation of the ECG, flagging clinically relevant ECG abnormalities based on a pre-defined set of abnormality criteria. Reports with pre-defined abnormalities will be sent to both the Principal Investigator and Sponsor or a designee.

If potentially clinically significant findings are detected by the Investigator or by the central reading, a local cardiologist should be consulted. All communications and diagnoses should be filed in the source documentation file.

Any ECG finding that is judged by the Investigator as a clinically significant change compared with baseline will be considered an AE, recorded and monitored.

The final decision whether the ECG findings are of clinical significance is the Investigator's responsibility.

## 9.9.5 Pregnancy Test

Pregnancy should be avoided during study and one month after discontinuing treatment. All females of childbearing potential must practice a highly effective method of contraception throughout the study period and for 1 month after treatment discontinuation. Methods that can achieve a failure rate of less than 1% per year when used consistently and correctly are considered as highly effective birth control.; see Section 6.1).

Any subject who becomes pregnant during the study period must not receive additional doses of study drug.

Pregnancy test (Serum  $\beta$ -hCG) will be performed for women of childbearing potential during the Screening visit. During the study, a urine pregnancy test will be performed at every study visit and according to local regulations.

A woman that suspects pregnancy should perform a pregnancy test, report results to the Investigator and in the event of positive results, discontinue treatment.

Results of the pregnancy test will be documented on the pregnancy eCRF page.

## 9.9.6 Vital Signs

Vital signs will be performed at all scheduled and unscheduled visits.

- Heart rate
- Blood pressure (Diastolic, Systolic)
- Temperature
- Respiratory rate

Blood pressure and pulse will be recorded in a sitting position after resting for 5 minutes.

For any abnormal vital sign finding, further assessment should be performed as deemed necessary by the Investigator.

## 9.9.7 Physical Examinations

Physical examinations will be performed at Screening, Baseline, week 24, 48, 72 and every 24 weeks thereafter as well as at early termination/study completion.

- General Appearance
- Head, Ears, Eyes, Nose, Throat
- Thyroid
- Cardiovascular
- Respiratory
- Gastrointestinal

#### **ARMOR Study**

- Skin
- Musculoskeletal
- Nervous System
- Lymph Nodes

Clinically significant changes from the initial physical findings at screening observed in subsequent visits will be considered AEs and will be documented on the AE eCRF.

#### 9.9.8 Body Measurements

Body measurements will be measured at Screening, Baseline, week 12 and at every visit thereafter as well as at early termination/study completion.

- Body Weight
- Waist Circumference
- Height (measured only at Screening visit)

#### 10 SAFETY AND PHARMACOVIGILANCE

Safety assessments will consist of evaluating relevant medical history, AEs and SAEs, laboratory parameters including chemistry, hematology and coagulation, vital signs, ECG, physical examinations, and documentation of all concomitant medications and/or therapies. The methods and timing of safety assessments are provided in Section 2 and will be performed in accordance with the schedule in Table 3 and Table 4

The study will closely be monitored by an independent Data Monitoring Committee (DMC) according to a pre-defined DMC charter. The DMC will periodically meet (at least every 3-4 months) to assess the study progress and conduct, accumulated safety data, and as appropriate, pharmacokinetic and efficacy data.

The DMC can make recommendations regarding stopping or modifying the overall study. The DMC will convene on a regular basis and on an ad-hoc basis as outlined in the DMC charter.

The DMC will be composed of independent physicians with expertise in the liver field and other relevant experts. Members of the DMC cannot be investigators in the study. An external independent unblinded statistician will prepare the reports for review by the DMC.

During the study, pre-defined clinical outcome events, possible DILI events and major adverse cardiovascular events will be adjudicated by independent adjudication committees.

- Clinical Outcome Adjudication Committee (COAC) will adjudicate predefined clinical
  outcome events (all-cause mortality, liver transplant, progression to cirrhosis, change in
  MELD score to > 15 and hospitalization due to hepatic decompensation events)
- Cardiac Adjudication Committee (CAC) will adjudicate Major Adverse Cardiovascular Events (cardiovascular death, non-fatal myocardial infarction, non-fatal stroke), hospitalization for unstable angina or heart failure, and all-cause mortality. Event

definitions will be based on the Standardized Definitions for Cardiovascular Endpoint Events in Clinical Trials.

 Hepatic Safety Adjudication Committee (HSAC) will adjudicate hepatic safety events including cases of suspected DILI as well as non-endpoint hepatic/hepatobiliary SAEs

The DMC will be provided the outcome of the adjudication.

#### 10.1 Adverse Events

## 10.1.1 Definition of an Adverse Events

Any untoward medical occurrence in a patient or clinical investigation subject administered a pharmaceutical product and which does not necessarily have a causal relationship with this treatment. An AE can therefore be any unfavorable and unintended sign (including an abnormal laboratory finding), symptom, or disease temporally associated with the use of a medicinal (investigational) product, whether or not related to the medicinal (investigational) product.

The following medical events will be considered AEs:

- Any new medical condition, sign, symptom or disease or any worsening of pre-existing condition (in severity or frequency) following signing of ICF
- Worsening of a pre-existing disease should be recorded as an AE only if the presentation and/or outcome is more severe than would normally be expected from the normal course of the disease in this patient
- An abnormal result of diagnostic procedures including abnormal laboratory findings will be considered an AE if any of the below are met:
  - Results in subject's temporary or permanent discontinuation of treatment or withdrawal by the Investigator
  - Is associated with clinical signs or symptoms
  - Is considered by the physician to be of clinical significance
- Any procedural complication

The following events will not be considered AEs:

- A chronic condition diagnosed during screening will be recorded as medical history and not as an AE
- Pre-existing disease, condition or laboratory abnormalities present before study entry (ICF signature) that does not worsen during the study
- Pre-planned elective hospital admission (planned prior to the study enrollment) for treatment or diagnostic procedure of a pre-existing condition, that has not significantly worsened
- A biopsy performed as part of the study is not considered an AE and hospitalization for liver biopsy, when required as standard of care for liver biopsy, and without complications is not considered an SAE

- Medical or surgical procedures are not considered AEs, rather, the condition leading to the procedure is the AE (e.g. anemia and not blood transfusion, appendicitis and not appendectomy)
- Abnormal laboratory values that in the Investigator's opinion are not clinically significant and do not require any intervention should not be reported as AEs

## 10.1.2 Recording and Reporting Adverse Events

AEs fall into the categories of "nonserious" and "serious". All AEs must be recorded on source documents and eCRF from the time the subject has signed the informed consent until the EoS or early termination (ESD) visit, regardless of apparent causality from use of the study drug.

At each visit, subjects should voluntarily report any AEs in response to general nonleading questions (e.g., "How have you been feeling since your last visit?"). For each AE reported by subjects, clinical site personnel should obtain all required information to complete the eCRF.

The AE term, date of onset, severity, seriousness, action taken, Investigator opinion of relationship to the study drug, outcome and date of resolution will be recorded in source documents and eCRF following the Investigator's assessment. If an ongoing AE worsens or improves in its severity, the maximum severity that occurred over the duration of the event should be recorded in eCRF.

AE verbatim terms provided by the Investigator will be coded using the current Medical Dictionary for Regulatory Activities (MeDRA) Version.

AEs classified as serious must be recorded on the appropriate SAE form and reported using the expeditious handling of SAE procedures to comply with regulatory requirements (see Section 10.1.5.3).

#### 10.1.3 Severity of an Adverse Event

Severity of AEs should be assessed by the Investigator according to Common Terminology Criteria for Adverse Events (CTCAE) definitions as follows:

- Grade 1: Mild; asymptomatic or mild symptoms; clinical or diagnostic observations only; intervention not indicated.
- Grade 2: Moderate; minimal, local or noninvasive intervention indicated; limiting age
  appropriate instrumental activities of daily living (ADL; which refers to preparing meals,
  shopping for groceries or clothes, using the telephone, managing money, etc.).
- Grade 3: Severe or medically significant but not immediately life-threatening; hospitalization or prolongation of hospitalization indicated; disabling; limiting self-care ADL (which refers to bathing, dressing and undressing, feeding self, using the toilet, taking medications, and not bedridden).
- Grade 4: Life threatening consequences; urgent intervention indicated.
- Grade 5: Death related to AE.

A Semi-colon (;) indicates 'or' within the description of the grade.

Severity is not synonymous with seriousness. For example, a severe headache is not necessarily an SAE. However, mild chest pain may result in a day's hospitalization thus meeting serious criteria and would be considered an SAE.

#### 10.1.4 Relationship of an Adverse Event to the Study Drug

The relationship of an AE to the study drug should be assessed by the Investigator using clinical evaluation and the following classification and considerations:

**No reasonable possibility - not related:** There is not a reasonable possibility that the administration of the study intervention caused the event or there is no temporal relationship between the study intervention and event onset, or an alternate etiology has been established.

**Reasonable possibility - related:** The AE is known to occur with the study intervention or there is a reasonable possibility that the study intervention caused the AE or there is a temporal relationship between the study intervention and event.

Reasonable possibility means that there is evidence to suggest a causal relationship between the study intervention and the AE.

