# 10.2 Safety Reporting to Investigators, Institutional Review Boards or Independent Ethics Committees, and Regulatory Authorities.

Sponsor or its designee is responsible for reporting all applicable SAEs to Regulatory authorities, Investigators, and IECs/IRBs, as applicable, in accordance with national regulations in the countries where the study is conducted.

Suspected Unexpected Serious Adverse Reactions (SUSARs) should be reported as expedited safety reports to all participating Investigators, ethics committees, and applicable regulatory authorities in accordance with ICH guidelines and the local regulatory requirements. The SUSARs will be submitted within 7 days for fatal and life-threatening events and within 15 days for other SUSARs events.

The Sponsor should submit all safety updates and periodic reports to the regulatory authorities, as required by applicable regulatory requirements.

Investigators should report to their local IEC/IRB as dictated by their board's policies and procedures.

The blinding will be maintained for the team who are involved directly in the study. For SUSAR reporting, dedicated personnel may break the subject's code without revealing the blind to the Sponsor personnel, its designee or site team.

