#### 11.3.1 Adverse Events

An AE is any untoward medical occurrence in a subject administered a pharmaceutical product, regardless of whether it has a causal relationship with this treatment. In this study, any AE occurring after the subject has signed the ICF should be recorded and reported as an AE.

The MedDRA dictionary will be used to standardize the terms used by the Investigator to describe the AEs.

The following will be incorporated into the analysis of adverse events:

- As analysis of AEs can incorporate only coded AEs, it is mandatory that at the time of database lock all AEs will be coded.
- Adverse events analyses will include only the Treatment Emergent Adverse Events
  (TEAEs), namely, those events which started on the day of randomization or afterwards.
  AEs lacking start day will be considered as TEAE.
- Analyses of TEAEs will include the display of cumulative incidence proportions (no. of subjects reporting at least one TEAE per category), exposure adjusted incidence rates of the number of TEAEs, and estimated differences and confidence intervals for all pairwise treatment arm comparisons.

The following analyses which are pre-planned for adverse events will include:

- Most frequent TEAEs (>5% of subjects in at least one study arm) by Preferred Term (PT).
- TEAEs broken down by System Organ Class (SOC) and by SOC and PT according to MedDRA dictionary.
- Serious TEAEs by MedDRA SOC and PT, data listing as well as summary table of SAEs broken down by study trimesters (90 days each).
- TEAEs broken down by severity.
- TEAEs broken down by relationship to study drug.
- TEAEs broken down by action taken.
- TEAEs broken down by event outcome.
- TEAEs will be provided broken down by study group and subgroups.
- Adverse Events dictionary used to code Investigator's verbatim terms will also be provided.
- Individual subject listings of TEAEs and non-TEAEs.

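### Section 10.1.4 lets timing alone make an adverse event related, contradicts its own definition of reasonable possibility, and does not say which category prevails when both apply

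*Combined protocol and SAP*

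**What the plan says.** Section 10.1.4 of the combined protocol and SAP uses a two-category scale. Relationship "should be assessed by the Investigator using clinical evaluation and the following classification and considerations".

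- **Related** is met on any of three grounds joined by *or*. The first two are: "The AE is known to occur with the study intervention or there is a reasonable possibility that the study intervention caused the AE". The third is: "or there is a temporal relationship between the study intervention and event".
- **Not related** is also an *or* list. Its first ground is that causation is not reasonably possible. The other two are: "there is no temporal relationship between the study intervention and event onset, or an alternate etiology has been established".
- A closing sentence defines the key term: "Reasonable possibility means that there is evidence to suggest a causal relationship between the study intervention and the AE".

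The classification is used in several places. Section 10.1.2 has the investigator's opinion on relationship recorded for every adverse event. Section 11.3.1 plans a table of "TEAEs broken down by relationship to study drug". Section 10.2 requires SUSARs to be sent to investigators, ethics committees and authorities, within 7 days if fatal or life-threatening and within 15 days otherwise. It also states: "For SUSAR reporting, dedicated personnel may break the" individual subject's code, with sponsor and site staff kept blinded.

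**The concern.** A temporal relationship is normally one consideration in judging causality. Here it is written as sufficient. Under continuous dosing almost any on-drug event has some temporal relationship with treatment, so this ground separates little. The closing definition asks for evidence pointing to causation, which timing alone does not supply. One section therefore sets two incompatible thresholds.

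The stake is the consistency of causality coding across about 200 sites (Synopsis) in a registrational trial. Two investigators can code the same event differently and both comply. The relationship table then mixes two standards, and the pool of serious events treated as suspected reactions depends on which sentence a site follows.

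**Working it through.** The plan states no figure that depends on this rule, so the main check is one of logic. Label the grounds as follows.

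- Related: R1 known to occur with the drug; R2 reasonable possibility of causation; R3 temporal relationship.
- Not related: N1 no reasonable possibility; N2 no temporal relationship; N3 another cause established.

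| Event | Related grounds met | Not-related grounds met | Result |
|---|---|---|---|
| On drug, evidence of causation, no other cause | R2, R3 | none | related only |
| On drug, no causal evidence, no other cause found | R3 | N1 | both |
| On drug, other cause established | R3 | N3 | both |
| After stopping, no temporal link, no causal evidence, not a known effect | none | N1, N2 | not related only |

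Rows 2 and 3 are the defect. In both, R3 alone puts the event in the related category. Row 2 needs no special circumstances: it is the ordinary unexplained event during treatment. Section 8.4.1 (twice-daily dosing) and section 8.1 (up to 7 years on the same assignment) give ample room for such events. I found no sentence in sections 10 or 11 that ranks the categories.

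**Can the excess be sized?** The number of extra subjects handled as SUSAR cases would be roughly

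excess = (subjects with an SAE) × (share unexpected) × (share related with R3 − share related under the closing definition).

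Only the first factor can be approximated, by carrying over the Phase 2b frequency in section 3.2: about 10% of subjects, with 65 weeks in the study (52 on treatment plus 13 of follow-up).

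- Over a similar period: 2000 × 0.10 = 200 subjects, split 2:1 into about 133 Aramchol and 67 placebo.
- Constant rate, 65-week basis: −ln(0.90)/1.25 = 0.084 per year. By 3 years 1 − exp(−0.084 × 3) = 22%, about 450 of 2000. By 5 years 1 − exp(−0.084 × 5) = 34%, about 690.
- Constant rate, 52-week basis: −ln(0.90) = 0.105 per year, giving 27% (about 540) and 41% (about 820).

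These are subjects with any SAE. They would occur under any relatedness rule, and the 3- and 5-year figures assume that all 2000 are followed that long. They bound the pool exposed to the ambiguity and do not measure its effect. For example, if another cause were established for an assumed 0% to 90% of the 200, and those events were then coded not related, between 200 and 20 subjects would remain, before the test of unexpectedness. The documents give neither the share with another cause nor the share unexpected.

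**The case against.** A reader might infer that nearly every event in the trial becomes related, that the relationship table is emptied of meaning, and that many subjects are needlessly unblinded. The documents do not support this, for four reasons.

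- **Same section.** The category is headed by reasonable possibility, which the section defines causally. The investigator is told to use clinical judgement. An event also counts as not related if "or an alternate etiology has been established". A sensible investigator could read the whole and never classify on timing alone.
- **Off-drug events.** Section 8.1 keeps subjects who stop treatment in follow-up, and section 11.3.1 counts every event from randomization onward. Some tabulated events will therefore lack a temporal link.
- **Other safety analyses.** The incidences, exposure-adjusted rates and between-arm differences for treatment-emergent events in section 11.3.1 do not depend on relatedness. Suspected liver injury and major cardiovascular events are adjudicated, and an unblinded DMC reviews the data (section 10).
- **Unblinding.** A SUSAR must also be serious and unexpected (section 10.1.5.2 defines the latter). Sections 8.4.3 and 10.2 confine the code break to dedicated personnel. Withdrawal after unblinding is stated for emergency code breaks, not for SUSAR reporting. Late SAE reporting in section 10.1.5.3 uses its own causal wording and does not invoke the temporal ground.

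All of this limits the consequences. None of it removes the contradiction. Clinical judgement is to be used together with the classification, so it does not override it. The other-cause exit and the closing definition are what create the overlap, because nothing says that they prevail over the temporal ground.

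**Conclusion.** The point holds as an internal contradiction with overlapping categories, and section 10.1.4 is wrong as written. On its literal terms timing is sufficient for related, against the section's own definition, and two common kinds of on-drug event fall into both categories with no tie-break.

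The effect is a relationship table that is over-filled and inconsistent between sites, and possibly more serious unexpected events handled as SUSARs. Its size cannot be estimated from the documents; it depends on how many sites apply the temporal ground and on the two shares missing above. Overall treatment-emergent event comparisons, the efficacy endpoints and alpha are not touched. Confidence is high on the text and low on the extent of the practical effect.

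**What to change.** In section 10.1.4:

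1. Delete the stand-alone temporal ground and make temporal plausibility a supporting condition, joined by *and* to evidence of causation.
2. Leave the known-to-occur ground as it is, unless its removal is proposed and justified separately.
3. State that an event with an established alternate cause is not related, whichever other ground it meets.

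Step 1 resolves row 2 of the table. Steps 1 and 3 together resolve row 3. A known effect with no temporal link would still meet R1 and N2, so the same tie-break sentence could usefully cover that case.

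Align the eCRF and SAE form guidance with the new text. Section 5.1 shows that subjects have already been randomized, so events already classified on timing alone should be re-queried under the corrected rule; otherwise the table will hold two standards. The cost is about one sentence of protocol text, form guidance, and a small amount of site retraining and query work.
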